1.3 SCHEDULE OF ACTIVITIES

Table 1. Schedule of Activities for NDURE and Usual Care and Follow-up

	Pre-screening	Visit 1	Visit 2 (Pre-Op)	Visit 3 (Pre-Discharge)	Visit 4 (Post-Discharge)	Visit 5 (Start of PORT)
Informed Consent						
Electronic Medical Record (EMR) Review Eligibility	X					
Informed Consent		X				
Study Procedures						
Randomization		X				
Demographics		X				
Clinical and Oncologic History		X			X	X
PORT Delay Nomogram		X				
Cultural Factor Survey		X				
Monitoring						
AE/SAE Assessment			X	X	X	X
Intervention Administration						
NDURE or UC			X	X	X	
Efficacy Evaluation						
PORT Delay						X
Feasibility						
NDURE Accrual	X					
NDURE Completion						X
Navigator Caseload		<----->				
Navigator Time Allocation		<----->				
Acceptability						
Satisfaction with the Interpersonal Relationship with the Navigator Scale						X
Satisfaction with Logistical Aspects of Navigation Scale						X
Program Evaluation						X
Cancer Care Delivery Processes						
Timely Care Processes		<----->				
Health Behavior Constructs						
Barrier Reduction				X	X	X
Unresolved Barriers			X	X	X	X
Care Transition Measure-15				X	X	

Interpersonal Support Evaluation List-12		X				X
Perceived Susceptibility Questionnaire		X		X	X	
Illness Perception Questionnaire-Revise Consequences Subscale		X		X	X	
Perceived Barriers Questionnaire		X		X	X	X
Communication & Attitudinal Self-Efficacy Scale-Cancer		X				X
Navigator Barrier Log		X		X	X	X

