4.2 RCT OF NDURE VERSUS USUAL CARE

4.2.1 OVERALL DESIGN

We will conduct a single-site, non-blinded, parallel-group, RCT of NDURE versus usual care for the management of delays and racial disparities starting PORT in adults with surgically-managed, locally advanced HNSCC. The study is designed to test the following hypotheses: 1) NDURE will result in a lower rate of delayed PORT relative to usual care (primary objective) and 2) NDURE will result in a smaller difference in PORT delay between AA and whites relative to usual care (secondary objective). The statistical plan for this between-group design analyzes the superiority of NDURE relative to usual care, although our power analysis is calculated with $\alpha = 0.1$ and $1 - \beta = 0.8$ based on the desire to emphasize power over type I error at this early stage of development (single-site pilot RCT) to ensure follow-up on promising interventions.

Upon enrollment and completion of the baseline assessments, patients will be randomized 1:1 to NDURE or usual care using a permuted block randomization method, with randomly selected block sizes of 2 or 4. Randomization, which will occur at the individual patient level, will be stratified with a 1:1 allocation ratio with strata defined by race (white, AA) and location of radiation facility (MUSC, non-MUSC) because of the known association of these variables with PORT delay^{6,33}. Furthermore, to facilitate evaluation of PORT delay rates in racial subgroups, we will oversample AAs for a final sample size of 50 white and 25 AA patients in each arm (see details in **Section 9.4.6, Sub-Group Analyses**). Given the impossibility of delivering the NDURE intervention in a non-blinded fashion, allocation concealment will be non-blinded. The study statistician ([name]) will generate the randomization schema and

randomization list. The study coordinator will implement the randomization. Randomization errors will be handled as per the modified intention-to-treat (ITT) population for the efficacy analysis.

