Cultural Factor Survey Scores is reported as the total score for each of the three individual subscales. The Cultural Factor Survey is a validated, psychometrically sound questionnaire consists of three subscales assessing temporal orientation (5 items), collectivism (6 items), and religiosity (9 items)⁵⁶. Prior PN studies have used these scales to measure cultural factors⁵⁷. Items are scored on a 4-point Likert scale from 'Strongly Disagree' (1) to 'Strongly Agree' (4). Scores on each sub-scale range from 5-20 (temporal orientation), 6-24 (collectivism), and 9-36 (religiosity). Higher scores on each subscale indicate greater amounts of each of the measured construct.

PORT Nomogram is a validated risk-prediction tool to estimate a personalized pre-treatment risk of PORT delay⁵⁸.

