9.4 STATISTICAL ANALYSES

9.4.1 GENERAL APPROACH

We will construct graphical displays and calculate descriptive statistics (e.g. frequencies and percent for categorical variables, and mean, median, standard deviation, and range for continuous variables). Covariates will be specified below. For inferential tests, we will use a p-value of 0.05, two-sided, and 95% confidence intervals (CIs) to assess statistical significance (Type I error). Covariates will be pre-specified as described below. Normality of the data will be assessed before underlying statistical procedures will be performed. We will evaluate variable transformations as needed to satisfy assumptions and consider transformations of variables to induce approximate normality and stabilize variance as needed. Nonparametric tests will be applied when appropriate.

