9.4.2.2 RCT OF NDURE VERSUS USUAL CARE

For the primary endpoint (delays starting PORT as defined in **Section 8.1, Endpoint and Other Non-Safety Assessments**), we will calculate the percentage of patients who start PORT > 6 weeks after surgery and corresponding 95% confidence interval (CI) for both arms and for white and AA subgroups within each arm in the efficacy analysis population. The rate of PORT delay will be compared between arms using a Mantel-Haenszel test of two proportions, with strata defined by race and location of radiation facility.

Every effort will be made to minimize missing data and lost-to-follow-up participants. Participants will complete assessments at baseline and post intervention using an iPad-based REDCap collection method. The program coordinator will attempt to contact patients at least three times using a variety of methods of communication (e.g. text message, phone call, email, mail, etc) to complete outcome measures. This method resulted in 100% instrument completion in prior studies conducted by our team.

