10.4 PROTOCOL AMENDMENT HISTORY

Table 4. Protocol Amendment History			
Version	Date	Description of Change	Brief Rationale
1.1	7/26/19	
 -Removed 10th floor from location of ICF process -removed language about ability to provide informed consent and adhere to study regimen from inclusion criteria 	
 -changes requested by MUSC IRB
2.0	9/27/19	
 -updated objectives to specify comparison of NDURE with UC -created more comprehensive and specific SoA -removed neoadjuvant therapy; added synchronous malignancy to exclusion criteria -removed MDASI-HN -added NIH confidentiality vocab 	
 -enhance clarity of objectives -more transparent SoA -improve clinical relevance of target population -improve clinical workflow -NIH compliance
3.0	12/16/19	
 -replaced [name] with [name] on study team -updated SOA -added white or AA race to inclusion criteria -clarified stratified sampling and stratified randomization -rename barrier load survey -harmonized staging information in inclusion criteria with mod ITT population 	
 -[name] left MUSC/HCC -more precision; address accidental overlap between visit 1 and 2 -internally harmonize protocol -previously mis-reported as stratified randomization across two strata -clarity for study assessment -internally harmonize protocol
4.0	2/26/20	
 -allowed use of telemedicine for NDURE sessions 1 or 3 -added NDURE nomogram -clarified that comorbidity will be measured using ACE-27 	
 -COVID-19 -assess pre-treatment risk of PORT delay -previously not specified

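### The pre-treatment risk score for PORT delay is left out of the primary between-arm analysis, which also has no effect estimate with CI: a missed efficiency, not an error

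*Combined protocol and SAP*

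**What the plan says.** Section 8.1, under Covariates, describes the PORT nomogram as a "validated risk-prediction tool to estimate a personalized pre-treatment risk of PORT delay". The table in Section 1.3, titled "Schedule of Activities for NDURE and Usual Care and Follow-up", has a row "PORT Delay Nomogram" marked at Visit 1, the visit at which randomization takes place. Section 10.4 records the change "added NDURE nomogram" under version 4.0, dated 2/26/20.

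In Section 9.4.2.2 the PORT delay rate is "compared between arms using a Mantel-Haenszel test of two proportions, with strata defined by race and location of radiation facility". That section gives a percentage with a 95% CI for each arm, and for white and AA patients within each arm. It specifies no difference or ratio between arms with a CI. Section 4.2.1 explains that the two strata were chosen "because of the known association of these variables with PORT delay".

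Section 9.4.1 says "Covariates will be pre-specified as described below", but no covariate list follows for the primary endpoint. The Section 8.1 covariates are called on once, in Section 9.4.3.2, where a logistic regression relates unresolved barriers to PORT delay. That is not a comparison of the arms.

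**The concern.** A baseline score built to predict the primary endpoint is the natural covariate for the primary comparison. The protocol's reason for stratifying by race and facility, their association with delay, applies equally to a score made for that purpose. No reason is given for leaving it out.

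Two things are at stake. The first is precision: with 75 patients per arm, adjusting for a predictor that adds to the strata narrows the interval. It also protects against chance imbalance in prior risk. Race and facility are balanced by design, but other sources of risk are not, and the modified ITT set is settled only after surgery and pathology.

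The second is the product of the trial. Section 4.2.2 justifies the randomized design partly by the precise effect size it should supply for a phase III trial. A Mantel-Haenszel test with separate arm percentages does not by itself deliver that number.

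**Working it through.** **Inputs from the documents.** 75 patients per arm, 45% delay under usual care, 25% under NDURE, two-sided alpha 0.10, stated power 83% (Section 9.2.2); 50 white and 25 AA patients per arm and 1:1 allocation (Section 4.2.1).

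**Inputs that had to be assumed.** The documents do not give the nomogram's AUC, its predictors, the facility split, or the strength of race and facility as predictors. The facility split was set at 50:50. Odds ratios for delay were 1.3 (AA) and 1.5 (non-MUSC) in scenario A, and 1.5 and 2.5 in scenario B. The AUC was varied.

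**Step 1: the plan's own figure.** Mean rate = (0.45 + 0.25)/2 = 0.35.
- Null SE = √(2 × 0.35 × 0.65 / 75) = 0.0779
- Alternative SE = √((0.45 × 0.55 + 0.25 × 0.75) / 75) = 0.0762
- Power = Φ[(0.20 − 1.645 × 0.0779) / 0.0762] = Φ(0.94) = 82.7%

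Exact enumeration of the unstratified Mantel-Haenszel statistic gives 83.3%. The stated 83% reproduces.

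**Step 2: closed form.** If the score explains a share R² of outcome variance beyond the strata, the effective size is 75/(1 − R²) per arm.

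| R² beyond strata | Effective n per arm | Power |
|---|---|---|
| 0 | 75.0 | 82.7% |
| 0.02 | 76.5 | 83.4% |
| 0.05 | 78.9 | 84.4% |
| 0.10 | 83.3 | 86.1% |
| 0.20 | 93.8 | 89.5% |

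**Step 3: simulation against the planned test.** There were 5,000 trials per setting, so the Monte Carlo SE is about √(0.85 × 0.15 / 5,000) = 0.5 point. Each trial had 50 AA and 100 white patients, stratified 1:1 allocation and marginal rates of 45% and 25%. The logit of risk was the strata effects plus an independent normal component. The stratified Mantel-Haenszel test was compared with the standardised risk difference from a logistic model with arm, strata and score, using an influence-function SE.

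| Scenario | AUC of score | Stratified MH | Standardised risk difference |
|---|---|---|---|
| A, score repeats strata | 0.566 | 82.9% | 83.1% |
| A | 0.625 | 83.9% | 84.9% |
| A | 0.690 | 83.5% | 86.8% |
| A | 0.745 | 83.7% | 88.7% |
| A | 0.803 | 83.6% | 91.5% |
| B, score repeats strata | 0.633 | 84.1% | 84.2% |
| B | 0.669 | 84.3% | 85.6% |
| B | 0.715 | 84.0% | 87.2% |
| B | 0.759 | 83.3% | 88.9% |
| B | 0.812 | 83.9% | 91.9% |

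An AUC near 0.63 yields about one point in scenario A and nothing in scenario B. The AUC alone does not settle the gain; only what the score adds to race and facility counts.

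**Step 4: type I error.** With both arms at 45%, the standardised risk difference rejected in 10.0% and 9.8% of trials (score AUC 0.69 and 0.80), and the Mantel-Haenszel test in 9.7% and 10.0%, at nominal 10%.

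**Step 5: why a risk difference.** The marginal odds ratio is (0.25/0.75)/(0.45/0.55) = 0.41. Conditional on the score it becomes exp(−1.08) = 0.34 at AUC 0.745 and exp(−1.22) = 0.30 at AUC 0.803. Reporting the adjusted odds ratio would therefore change the quantity estimated. Standardising to a risk difference keeps the 20-point contrast on which the trial was sized.

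**The case against.** The strongest defence is that nothing is wrong with the plan. Section 9.2.2 ties the Mantel-Haenszel test to the stratified design, analysing as randomized is sound, and 83% exceeds the plan's 80% target. This stands.

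Four stronger readings are tempting, and the documents do not support them.
- A reader might infer a definite loss of power. No AUC or predictor list is given, and validated does not mean strongly discriminating. Section 2.2.3 names race and fragmented care among the factors associated with delay, so overlap with the strata is plausible, though it cannot be checked. Measuring the gain from an unadjusted comparison would also mislead, because the planned test already adjusts for both strata.
- A reader might say that adjustment is free. It needs no new data, but a Mantel-Haenszel test cannot take a continuous score without categorising it. A model, a variance method and a missing-score rule must be fixed in advance.
- A reader might say that every patient has a score. The schedule plans this, but the score entered in version 4.0 and the documents do not say whether RCT patients enrolled earlier.
- A reader might say that the score is never used. It falls within the Section 8.1 covariates of the unresolved-barriers regression.

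Chance imbalance is also partly covered: two predictors are balanced by design, and Section 9.4.4 compares baseline characteristics. That comparison describes imbalance; it does not adjust the estimate.

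**Conclusion.** The point holds as a missed efficiency. A pre-treatment predictor of the primary endpoint is scheduled in both arms and plays no part in the primary between-arm analysis, which also specifies no effect estimate with CI. Validity and the stated power are not in question.

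The gain is about 1 to 6 points of power for an assumed AUC of 0.63 to 0.76, about 8 points near 0.80, and nil if the score only repeats race and facility. These figures assume 75 analysed patients per arm, a score available for all of them and linear on the logit scale, and the assumed strata effects. Losses to follow-up counted as delayed were not modelled and could weaken the score's association with the outcome.

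All power figures use two-sided alpha 0.10, as in Sections 4.2.1 and 9.2.2. Section 9.4.1 states 0.05 for inferential tests, at which the design has 73.3% power by the Step 1 formula. That difference of 9.4 points exceeds the likely gain here. It is a separate matter, and the sections must be reconciled. The case for a between-arm estimate with CI does not depend on the AUC.

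**What to change.** Before outcome data are seen, add to Section 9.4.2.2 a standardised (g-computation) risk difference with CI, from a logistic model with arm, race, planned radiation facility and the logit of nomogram risk. Make it the primary effect estimate, or the key supporting estimate beside the stratified Mantel-Haenszel test. Retain that test in either case.

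The SAP should also state:
- the variance method, for example an influence-function SE or a bootstrap within strata;
- a rule for missing scores that uses neither arm nor outcome. For any patient enrolled before version 4.0, compute the score from baseline records where its inputs exist, with a stated fallback such as the stratum mean plus a missing indicator;
- if the score is left out after all, the reason.

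The model is small for the data: 75 × 0.45 + 75 × 0.25 = 52.5 expected delays for four terms besides the intercept. The cost is more SAP text, one regression and reliance on a model-based estimate. No new data collection is needed.

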8.2 ADVERSE EVENTS AND SERIOUS ADVERSE EVENTS

8.2.1 DEFINITION OF ADVERSE EVENTS

This trial is considered to carry a low risk to subjects (i.e. has a “no more than minimal risk” designation). As such, this protocol defines an adverse event (AE) as any undesirable sign, symptom, medical, psychological, social, or emotional reaction that is definitely, probably, or possibly related to the study intervention.

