2.3 RISK/BENEFIT ASSESSMENT

2.3.1 KNOWN POTENTIAL RISKS

Overall, this research study poses no more than minimal risks to participants. There are no physical, financial, legal, social, or cultural, risks to the study participants by joining this study. There are slight

psychological risks, as described below. There is a slight risk that subjects may experience adverse psychological reactions such as anxiety or stress as a result of discussing issues related to cancer or barriers to cancer care. We believe that this risk is minimal. We are using survey items that are commonly used in clinical settings and subjects are likely to have had prior exposure to similar types of questions as part of their medical care. Furthermore, in our past studies with white and AA men and women with HNSCC, the overwhelming majority of respondents have said they found the questions that we have asked related to care have not been upsetting.

There is also a slight risk that confidential information about the participant may be accidentally disclosed as study participants may be asked to provide information considered confidential or private during study interviews. The likelihood of this risk is low as all the investigators have been involved in similar research in the past and have not experienced this problem before due to adequate safeguards.

The decision to participate in this research will be voluntary and individuals may refuse to take part or choose to stop taking part at any time. Participants will also be encouraged to take their time when answering questions and may decline to answer any question at any time. If patients become upset talking about their cancer and the barriers that they faced, they will be offered a referral to the Hollings Cancer Center (HCC) Behavioral Medicine program (which is covered by most health insurance programs) or the HCC Social Worker who will offer links to other HCC and community resources.

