2.3.3 ASSESSMENT OF POTENTIAL RISKS AND BENEFITS

The decision to participate in this research will be voluntary. Participants will be informed that they can stop participating at any time and/or refrain from answering any questions that make them uncomfortable. The interviewers are trained researchers with experience conducting interviews related to cancer. By using survey items that are commonly used in clinical settings (to which subjects have likely had prior exposure as part of their medical care) we will minimize psychological risk. If a participant has a psychological adverse event (AE) talking about his/her cancer and/or the barriers that he/she faced during treatment, the participant will be offered a referral to the HCC Behavioral Medicine program (which is covered by most health insurance programs) or the HCC Social Worker who will offer links to other HCC and community resources as detailed in the Data and Safety Monitoring Plan. Immediate backup and support will be available.

To help ensure and protect privacy of participants and confidentiality of research data for the study, we will assign a unique study ID number to each subject's information in place of his/her name and will label data collection forms with the ID number. All hard copy and electronic files will be stored appropriately using double-locked methods and password-protection. Only the study team members will have access to study records. Participant data will be collected and recorded on either a password-protected electronic data capture format (REDCap) or paper-based forms depending upon patient preference. For the paper

collection data method, the data collection form will be labeled only with the participant's unique study ID number, and then stored within locked drawers in a locked office.

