8.2.3.2 RELATIONSHIP TO STUDY INTERVENTION

All AEs will have their relationship to study procedures, including the intervention, assessed by the PI based on temporal relationship and his clinical judgment. The degree of certainty about causality will be graded using the categories below.

- **Definitely Related** – There is clear evidence to suggest a causal relationship, and other possible contributing factors can be ruled out. The clinical event, including an abnormal laboratory test result, occurs in a plausible time relationship to study procedures administration and cannot be explained by concurrent disease or other drugs or chemicals. The response to withdrawal of the study procedures should be clinically plausible. The event must be pharmacologically or phenomenologically definitive.
- **Probably Related** – There is evidence to suggest a causal relationship, and the influence of other factors is unlikely. The clinical event, including an abnormal laboratory test result, occurs within a reasonable time after administration of the study procedures, is unlikely to be attributed to concurrent disease or other drugs or chemicals, and follows a clinically reasonable response on withdrawal.
- **Possibly Related** – There is some evidence to suggest a causal relationship (e.g., the event occurred within a reasonable time after administration of study procedures). However, other factors may have contributed to the event (e.g., the participant's clinical condition, other concomitant events). Although an AE may rate only as "possibly related" soon after discovery, it can be flagged as requiring more information and later be upgraded to "probably related" or "definitely related", as appropriate.

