8.2.3.3 TIME PERIOD AND FREQUENCY FOR EVENT ASSESSMENT AND FOLLOW-UP

Recording/reporting of AEs will begin after the subject signs informed consent and end after the subject completes the intervention and follow up period as defined in the protocol.

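### The adverse event definition in 8.2.1 is tied to the intervention alone, which conflicts with 8.2.3.2 and 2.3.3, and no AE assessment is scheduled at Visit 1, where the baseline questionnaires are given

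*Combined protocol and SAP*

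**What the plan says.** - **Definition (8.2.1).** Because the trial is designated minimal risk, an AE is limited to an undesirable sign, symptom or "emotional reaction that is definitely, probably, or possibly related to the study intervention".
- **Collection (8.2.3.4).** AEs are collected and reported as that definition sets them out.
- **Causality grading (8.2.3.2).** "All AEs will have their relationship to study procedures, including the intervention, assessed by the PI". The three grades that follow (definite, probable, possible) are each worded by reference to study procedures.
- **Named risk (2.3.1).** The psychological risk is "anxiety or stress as a result of discussing issues related to cancer or barriers to cancer care". One reason given for calling it minimal is the choice of survey items: "We are using survey items that are commonly used in clinical settings".
- **Handling of distress (2.3.3).** In a paragraph on interviewers and survey items: "If a participant has a psychological adverse event (AE) talking about his/her cancer and/or the barriers that he/she faced during treatment", the participant is offered referral.
- **Recording window (8.2.3.3).** "Recording/reporting of AEs will begin after the subject signs informed consent".
- **Schedule of activities (1.3).** The AE/SAE row is marked at Visits 2, 3, 4 and 5. Consent, randomization and six patient questionnaires are marked at Visit 1.

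**The concern.** An AE definition decides what gets written down. If relation to the intervention is part of the definition, an event caused by some other part of the research is screened out before anyone grades its cause. The protocol relies on its survey items when it argues that the psychological risk is minimal, so it accepts that surveys can cause distress. Yet questionnaires are not part of NDURE or of usual care as section 6.1.1 describes them.

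At stake is whether the minimal-risk statement can be checked against recorded events. The monthly aggregate review in 10.1.6 sees the AEs that were logged, and clinical monitoring is listed as not applicable (10.1.7). Staff who follow 8.2.1 to the letter and staff who follow 2.3.3 would log different events for the same participant.

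**Working it through.** No arithmetic decides this point. The check sets the relevant sections side by side.

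**Step 1. Is a questionnaire part of the study intervention?** Section 6.1.1.1 and its Table 2 describe NDURE as three navigation sessions with a manual, a patient guide and system changes. Section 6.1.1.2 describes usual care as provider-led discussion of referrals. Questionnaires appear in neither. They are listed in 8.1 as assessments.

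**Step 2. Can distress from a baseline questionnaire be related to the intervention?** Section 4.2.1 places the baseline assessments before randomization in the RCT. The feasibility schema (1.2.1) likewise places the baseline questionnaires before enrollment into NDURE. At that moment no intervention has been received, so a reaction caused solely by those questionnaires cannot be even possibly related to it. Under 8.2.1 read literally it is not an AE, and under 8.2.3.4 it is not collected.

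At later visits the separation is less clean. Some questionnaires fall at the same visits as navigation sessions (Visits 3 and 4), so a reaction there could often be graded possibly related to the intervention. The gap is therefore clearest at baseline.

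**Step 3. Do other sections use the same anchor?**

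| Section | An event is tied to |
|---|---|
| 8.2.1 Definition | the study intervention |
| 8.2.3.2 Causality | study procedures, of which the intervention is one |
| 2.3.3 Risk assessment | talking about cancer or barriers, in a paragraph on interviewers and survey items |

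Section 8.2.1 uses the same three grades that 8.2.3.2 defines, but ties them to a narrower object. The three sections cannot all be followed as written.

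**Step 4. What is the source of the named risk?** Section 2.3.1 speaks of discussing cancer or barriers to care. Surveys are one such occasion. The navigation sessions are another, since the navigator elicits barriers and explains the consequences of delay (6.1.1.1 and Table 2). The documents do not divide the risk between the two.

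**Step 5. Schedule against recording window.** The questionnaires marked at Visit 1 are:

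1. Cultural Factor Survey
2. Interpersonal Support Evaluation List-12
3. Perceived Susceptibility Questionnaire
4. Illness Perception Questionnaire-Revised, Consequences subscale
5. Perceived Barriers Questionnaire
6. Communication & Attitudinal Self-Efficacy Scale-Cancer

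That makes six. AE/SAE assessments marked at Visit 1: none. The window is open from consent, which is also at Visit 1. A Visit 1 event could be picked up at the Visit 2 assessment, but only if it counts as an AE, which returns to Step 2.

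**Step 6. Do other reporting routes close the gap?** The SAE definition (8.2.2) has no relatedness condition, so a serious event is not lost, but ordinary anxiety or stress would not meet it. An unanticipated problem (8.3.1) must be unexpected and must suggest greater risk than was previously recognized. Distress of the kind 2.3.1 already names would usually fail that test. Neither route captures mild or moderate questionnaire distress.

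**The case against.** The best defense is that the wording is loose and that no exclusion was intended. Section 2.3.3 itself calls distress from talking about cancer or barriers an AE, and 8.2.3.2 grades relation to study procedures, so a sensible coordinator would log the event. The narrow definition is also a deliberate choice, tied to the minimal-risk designation. This stands as far as intent goes. A reader might infer from 8.2.1 that questionnaire distress can never be an AE under this protocol; 2.3.3 and 8.2.3.2 do not support that. What remains is a conflict between sections, and 8.2.1 is the one that 8.2.3.4 uses to decide what is collected.

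A second defense is that a recording window does not oblige a scheduled assessment on its first day. That is correct. The missing Visit 1 mark is the absence of a prompt and does not bar recording.

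Third, participants are not left without support. They may decline any question and are offered referral to behavioral medicine or social work (2.3.1, 2.3.3), and reasons for withdrawal are recorded (7.2). This stands too. The point concerns the record of events and not the care of the participant.

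A reader might also infer that the definition would leave almost no AEs in the usual-care arm and so distort a comparison of arms. The documents do not support this. They use the term intervention for both arms: usual care is described under the intervention heading (6.1.1.2), the schedule's intervention row reads NDURE or UC, and 9.3 speaks of the intervention as NDURE or usual care. Section 9 plans no comparison of AEs between arms.

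**Conclusion.** The plan is wrong as written, at minor severity. Section 8.2.1, taken literally and combined with 8.2.3.4, leaves out distress caused solely by study questionnaires. This conflicts with 8.2.3.2 and 2.3.3. The schedule adds a smaller gap, because no AE/SAE check is marked at the visit where six patient questionnaires are given.

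The conclusion rests on two readings: that questionnaires are not part of the study intervention, which 6.1.1 supports, and that the schedule's columns are as they appear in the extracted table, where the marks line up consistently across rows.

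No size can be put on the missed events. The documents give no rate of survey distress and describe it as slight. The number of questionnaires or items shows exposure and does not measure risk. A reader might infer that the named psychological risk comes mainly from the surveys, but 2.3.1 does not say so and the navigation sessions cover the same ground. The primary endpoint and its analysis are unaffected.

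**What to change.** Make two edits.

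1. In 8.2.1, widen the relatedness condition to read *related to the study intervention or any study procedure (e.g. questionnaires, interviews)*. This brings the definition into line with 8.2.3.2 and 2.3.3, and 8.2.3.4 then needs no change.
2. In the schedule of activities (1.3), mark AE/SAE assessment at Visit 1, after the baseline questionnaires, in line with the recording window in 8.2.3.3.

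The cost is one change of wording, one added mark in the schedule, and a few more mild events to log. The sample size and the statistical analysis do not change.
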